## 1. BACKGROUND

This Technical Document for Statistical Analysis (TDSA) provides the data-handling rules, derivation rules, and statistical methods of summarizing and analyzing the efficacy and safety data that will be used for the data analysis and the reporting of the results from **Part A** of study BP40283.

Recruitment rate in **Part A** has remained substantially below the original estimates despite the implementation of a protocol amendment and the addition of more sites. Therefore the Roche TAAR1 Project Team and the Clinical Team have decided to stop study Part A (monotherapy) and start Part B (add-on treatment). In total 27 patients have been randomized into **Part A**.

There will be a separate TDSA for **Part B** of the study.

## 2. STUDY DESIGN

This is a Phase 2, multicenter, randomized, double-blind, two-part, placebo-controlled, parallel-group study of 12 weeks of treatment in patients with schizophrenia or schizoaffective disorder. An overview of the study design is provided in [Figure 1](#). The study is designed to collect potential efficacy data as well as safety and tolerability data in a patient population.

This study is a proof of concept study (**Part A**) followed by a dose-ranging study (**Part B**): RO6889450 will first be evaluated in a monotherapy setting (Part A), i.e. the participants will withdraw from their antipsychotic treatment(s), then potential efficacy of two dose levels of RO6889450 in combination with usual antipsychotic treatments(s) will be evaluated.

For both Parts A and B randomization occurs on Day 1 (Baseline), after screening period including placebo compliance period (inclusive of one-week-wash-out period for Part A). Treatment will be allocated by stratified block randomization on the bases of the three (Part A) or four (Part B) factors: baseline Brief Negative Symptoms Scale (B NSS) avolition/apathy subscores ( $\leq 6$  vs.  $> 6$ ), age (18-35 years vs. 36-55 years), sex (Male vs. Female), and only for Part B antipsychotic treatment (full D2/5HT2A antagonist vs. partial D2 receptor agonist).

### Part A (monotherapy)

Participants will be washed out (one week) from their antipsychotic therapy before being randomized 1:1 to either [REDACTED] QD of RO6889450 or placebo for 12 weeks.

### Part B (add-on therapy)

Participants will be randomized 1:1:1 to [REDACTED] QD of RO6889450, [REDACTED] QD of RO6889450, or placebo for 12 weeks.

**Part B** of the study is designed to evaluate potential efficacy of two dose levels of RO6889450 as adjunct to usual antipsychotic treatment(s). Part B is planned to start after Part A. Participants who are enrolled in Part A cannot be screened for Part B.

### Length of Study

**Part A:** The total duration will be approximately 147 days (from screening through study completion) for each enrolled participant as follows:

- Screening up to 35 days (including the placebo compliance and a 7-day washout period)
- Treatment period: 84 days (12 weeks)
- Follow up: 28 days

[figure not shown]
**Part B:** The total duration will be up to approximately 147 days (from screening through study completion) for each enrolled participant as follows:

- Screening: up to 35 days (including the placebo compliance period)
- Treatment period: 84 days (12 weeks)
- Follow up: 28 days

### End of Study

The end of study is defined as the date when the last participant last observation (LPLO) occurs. LPLO is expected to occur approximately 28 days after the last participant's last dose.

Figure 1 Overview of Study Design

D2 = D2/SHT2A antagonists or D2 partial agonist; n = number of completers

## 2.1 PROTOCOL SYNOPSIS

The Protocol Synopsis is in Appendix 1. For additional details, see the Schedule of Assessments of Part A in [Appendix 2](#).

## 2.2 OBJECTIVES AND ENDPOINTS

The objectives and corresponding endpoints are provided in Table 1.

**Table 1 Objectives and Endpoints**

Objectives	Endpoints
Primary	
Part A: To compare the efficacy of [REDACTED] QD of RO6889450 as monotherapy with placebo on negative symptoms in patients with schizophrenia or schizoaffective disorder.	Part A & B: Change from baseline at Week 12 in the Brief Negative Symptoms Scale (BNSS) avolition/apathy subscore (sum of items "behavior" and "internal experience").
Part B: To compare the efficacy of [REDACTED] QD of RO6889450 as add-on therapy with placebo on negative symptoms in patients with schizophrenia or schizoaffective disorder.	
Secondary	
To compare the effect of RO6889450 with placebo on: 

Clinical Global Impression Severity (CGI-S) and Improvement (CGI-I) (overall and negative symptoms)

	

Change from baseline in CGI-S and CGI-S negative symptoms (CGI-S NS) scores

CGI-I and CGI-I negative symptoms (CGI-I NS) scores

To compare the effect of RO6889450 with placebo on: 

Symptoms of schizophrenia or schizoaffective disorder as assessed with the Positive and Negative Syndrome Scale (PANSS), BNSS, and Defeatist Performance Attitude Scale (DPAS)

	

Change from baseline in PANSS total and symptom factor scores

Change from baseline in BNSS total and subscores

Change from baseline in DPAS scores

Objectives	Endpoints
To compare the safety and tolerability of 12 weeks of treatment with RO6889450 as monotherapy (Part A) or add-on therapy with placebo (Part B).	
 
Incidence, nature, and severity of AEs
 
Incidence, nature, and severity of SAEs
 
Incidence, nature, and severity of treatment discontinuations due to AEs
 
Change from baseline in orthostatic vital signs recordings
 
Change from baseline in ECG intervals: heart rate, PQ (PR), QRS, QT, RR and QTcF along with information on T- and U-waves
 
Incidence of laboratory abnormalities, based on hematology, clinical chemistry, and urinalysis test results
 
Change from baseline in C-SSRS and Extrapyramidal symptom rating scale, abbreviated (ESRS-A)
 

To evaluate the PK of RO6889450 and RO6889450-derived metabolite(s).	
 
Concentration per time point
 
AUCss of RO6889450 and RO6889450-derived metabolite(s)
 
Cmax of and RO6889450-derived metabolite(s)
 
Other PK parameters as appropriate
 

Tertiary/Exploratory	
To explore the effects of RO6889450 on: 
 
Reward learning tasks (Effort-Choice Benefit (ECB) task; Reinforcement Learning Working Memory (RLWM) task)
 
	
 
ECB: Percentage of high effort choices under deterministic reward conditions for high reward magnitudes
 
RLWM Learning Phase: Proportion of correct choices in late trials and for large blocks of sizes
 
RLWM Testing Phase: Interaction 'value difference modulated by value mean' (assessing the 'choose A avoid B' paradigm).
 

To explore the effects of RO6889450 on: 
 
Overall functioning/cognition
 
	
 
Change from baseline in Brief Assessment of Cognition in Schizophrenia (BACS)
 
Change from baseline in adjusted total time as measured by the Virtual Reality Functional Capacity Assessment Tool (VRFCAT)
 

To explore the effects of RO6889450 on: 
 
Changes in smoking dependence
 
	
 
Change from baseline in Fagerstrom Test for Nicotine Dependence (FTND) total score
 

To explore the effects of RO6889450 on: 
 
Levels and patterns of social and general activity
 
To assess CYP2C19 status on PK parameters
 
	
 
Phone usage behavior data
 
Genotyping of CYP2C19
 

Objectives	Endpoints

 
Part A only: To assess effects on relapse prevention
 
	
 
Compare rate and timing of relapses and study withdrawal between placebo and RO6889450
 

## 2.3 DETERMINATION OF SAMPLE SIZE

In **Part A**, 50 evaluable participants per arm were planned to be randomized to obtain 80% power at the one-sided type I error of 0.05, assuming the true effect size of 0.5.

Based on data from previously conducted studies, the standard deviation for the primary endpoint, the change from baseline in the BNSS Avolition/Apathy Subscale at week 12 (consisting of the sum of the two items 'Avolition/Apathy: Behavior' and Avolition/Apathy: Internal Experience) is about 2.8. Hence, the effect size of 0.5 translates to a reduction (vs. placebo) of 1.4 points for the primary endpoint.

With the anticipated sample size of 50 participants per arm, at the one-sided type I error of 0.05, any observed reduction (vs. placebo) by approximately 0.92 or more points is expected to be statistically significant.

Assumign 20% of the participants randomized will not complete 12 weeks of treatment, in **Part A**, it was planned to randomize approximately 125 participants to one of two treatment arms to ensure that approximately 100 participants complete the 12 weeks of treatment period.

For sample size determination of **Part B**, please refer to the protocol.

## 2.4 ANALYSIS TIMING AND UNBLINDING

### 2.4.1 Interim Efficacy Analysis

No interim analysis will be performed for study **Part A**. Study **Part B** starts without interim analysis of **Part A** [REDACTED]

The Sponsor may choose to conduct an interim analysis of **Part B** to determine the chance of final success. The results of such an analysis may support an early termination of Part B. Interim analyses of **Part B** will be described in the TDSA of **Part B**.

### 2.4.2 Interim Safety Reviews

The independent Data Monitoring Committee (iDMC, see Section 3.3) will review unblinded safety and primary/secondary efficacy endpoint data, especially focusing on **Part A** which involves a one-week-wash-out period and only placebo arm.

Two safety reviews are scheduled for the review of the safety data accrued in **Part A** of the study:

1. Once approximately 10 participants per treatment arm reach the Week 2 visit, i.e., after the one-week-wash-out period. – This safety review was done at 14 November 2019, the recommendation was to continue the study without modification.
2. Once approximately 30 participants per treatment arm reach the Week 12 visit, i.e., during and after the Treatment Period with the main focus being on placebo arm. – This safety review will not be conducted as the Part A of the study was stopped before approximately 30 patients per treatment arm reached the Week 12 visit.

Additional safety reviews for the safety data may be conducted for study **Part B** at the request of the iDMC or the Study Team, e.g. if safety concerns arise.

The Sponsor's study statistician as well as statistical programmer will be unblinded to provide unblinded safety information to the iDMC. The data will be handled and cleaned in a secure area that is not accessible by any blinded SMT member.

#### **2.4.3 Final Analyses**

The final analysis of data from the trial will be performed separately for **Part A** and **Part B** when all patients of the respective study part have either completed the study or discontinued early from the study, all data of the trial are in the database, have been cleaned and verified, and the database has been locked.

### **3. STUDY CONDUCT**

#### **3.1 RANDOMIZATION**

An Interactive Voice/Web Response System (IxRS) is used to randomize the participants in equal proportion to the treatment arms.

In **Part A** treatment will be allocated by **stratified block randomization** on the basis of the following factors:

- Baseline BNSS avolition/apathy subscore ( $\leq 6$  or  $> 6$ )
- Age (18-35 years vs. 36-55 years)
- Sex (Male vs. Female)

In **Part A**, on Day 1 (baseline) participants within each block stratum are randomly assigned in 1:1 ratio to either [REDACTED] QD of RO6889450 or placebo. Approximately 125 participants will be randomized to ensure approximately 100 number of completers.

### **3.2 INDEPENDENT REVIEW FACILITY**

PANSS and BNSS will be assessed live via secure videoconference by an approved remote centralized rater. If a remote administration session cannot occur for an unforeseen reason, it will be rescheduled.

### **3.3 DATA MONITORING**

#### **3.3.1 Independent Data Monitoring Committee (iDMC)**

An iDMC will regularly review unblinded safety and efficacy (as appropriate) data. The iDMC will be composed of at least two psychiatrists external to the Sponsor and a statistician external to the Sponsor and will be responsible for monitoring safety data to help ensure that continuation of the trial in its current design does not pose unacceptable safety risks to participants. The iDMC will also assess safety as part of the planned interim safety analysis.

A separate iDMC charter documents the roles, responsibilities, membership as well as scope of activities, time of meetings, and communication plan. Planned and ad hoc safety reviews will be performed as described in the iDMC charter.

## **4. STATISTICAL METHODS**

The final analysis of data from the trial will be performed separately for **Part A** and **Part B**. This TDSA describes the analyses for **Part A**.

Data for study **Part A** will be listed and summarized descriptively. No formal hypothesis test will be performed.

### **4.1 ANALYSIS POPULATIONS**

For purposes of analysis, the following populations are defined in [Table 2](#).

**Table 2 Analysis Populations**

Population	Description
Modified intent-to-treat (ITT)	All randomized participants who have received at least one dose of study drug, including participants who were withdrawn prematurely, will be included in the efficacy population. The modified ITT analysis population will be the primary analysis population for all efficacy data analyses.
Per-protocol (PP)	No PP analysis population is defined for Part A
Safety evaluable (SE)	Same as modified ITT analysis population.

Pharmacokinetic (PK)	All participants who have received at least one dose of study drug and who have data from at least one post-dose sample will be included in the PK analysis population. Participants will be excluded from the PK analysis population if they significantly violate the inclusion or exclusion criteria, deviate significantly from the protocol, or if data are unavailable or incomplete that may influence the PK analysis. Excluded cases will be documented together with the reason for exclusion. All decisions on exclusions from the analysis will be made prior to database closure.
----------------------	--

## 4.2 ANALYSIS OF STUDY CONDUCT

### 4.2.1 Disposition of Participants

For all patients in the modified ITT analysis population enrollment in the study, discontinuation of study drug and from the study, and reason for discontinuation will be summarized per treatment arm to which participants are randomized. In addition, protocol violations will be summarized by treatment arm.

### 4.2.2 Overview of Analysis Population

The number (percentage) of participants excluded from the analysis populations will be summarized by reason for exclusion per treatment arm

### 4.2.3 Protocol Violations

The major protocol violations will be identified before database lock. The number and percentage of participants with major protocol violations will be summarized per protocol violation criterion and treatment arm to which participants are randomized.

## 4.3 ANALYSIS OF TREATMENT GROUP COMPARABILITY

The evaluation of treatment arm comparability between the two treatment arms in study **Part A** will include summaries of demographics, baseline disease characteristics, and participant medical history. Data will be summarized by treatment arm to which participants were randomized.

Descriptive statistics (mean, standard deviation, median, and minimum-maximum) will be presented by treatment arm for continuous variables. Frequency counts and proportions will be presented by treatment arm for categorical variables.

#### **4.3.1 Demographic Characteristics**

Summary tables of demographics will be produced for the modified ITT analysis population by treatment arm to which participants were randomized. The following variables will be summarized:

Categorical variables:

- Sex (Male vs. Female)
- Age group (18-35 years vs. 36-55 years) at baseline
- Race (Black or African American vs. White) or Ethnicity (Hispanic or Latino vs. non-Hispanic or Latino)

Continuous variables:

- Weight [kg], Height [cm], Body Mass Index (BMI) [kg/m^2] at baseline
- Age (years) at baseline

and others if appropriate.

#### **4.3.2 Baseline Disease Characteristics**

Baseline data for BNSS total- subscores, PANSS total- and symptom factor scores, CGI-S and CGI-S NS scores will be included in the respective efficacy outputs. No separate outputs will be presented for baseline.

#### **4.3.3 History of Schizophrenia**

Summary statistics will be generated for each treatment group and will include each patient's history of schizophrenia. The key variables from the electronic Case Report Form (eCRF) listed in the psychiatric history page will be summarized. The time (in months) since the diagnosis of schizophrenia and the time (in months) since the most recent hospitalization for worsening of Schizophrenia will be calculated relative to the randomization date.

#### **4.3.4 Previous and Current Diseases at Baseline**

For all diseases at baseline (other than schizophrenia), the term entered by the investigator describing the disease (the "verbatim term") will be assigned to a standardized term (the "preferred term") and System Organ Class from MedDRA. All analyses will be performed using these preferred terms and body systems. Diagnoses will be categorized by condition at baseline (ongoing with treatment/ongoing without treatment/resolved) with use of the responses from the medical history page of the eCRF.

The number and percentage of patients with previous (resolved) diseases will be summarized by treatment group. Diseases concurrent (ongoing with or without treatment) at baseline will be summarized similarly in a separate table. Multiple occurrences of a disease (i.e., same coded term) will be counted only once.

#### **4.3.5 Previous and Concomitant Treatments (Other than Study Medication)**

For all medications, the term entered by the investigator describing the medication (the “verbatim term”) will be assigned to a standardized term (the “preferred term”) and drug class from the WHO drug dictionary. All analyses will use these preferred terms and medication classes.

The number and percentage of patients who received previous or concomitant treatment (medication, medical procedure, or non-medical therapy) will be summarized by treatment group.

Multiple occurrences of a medication in an individual (i.e., same coded term) will be counted only once. All summary tables will be sorted by medication class (in decreasing order of overall incidence), then by preferred term (in decreasing order of overall incidence).

### **4.4 DEFINITION OF BASELINE**

Baseline for all efficacy and safety analyses is defined as the last non-missing value recorded prior to or on the first day of randomized double-blind study drug administration.

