Appendix 9 Evaluation to Sign Consent (example form)

_		Evaluation to Sign Cor	isent (ESC)	Form Version: 1/15/16 JM
M	PRCID#:	Program ID:		
Subject Initials:		Rater ID:	Rater Initials:	
Pr	otocol ID#:	Protocol Name:		
Ma		t regarding item 1 below. Ask the passe in asking the questions in order to		
IT	EMS:			SCORE
1.	Is the patient alert and al $yes = 2$ $no = 0$	ole to communicate with the examine	r?	
2.	-	at least two (2) potential risks incurred list potential risks, 1= able to list of	1 1 0	
3.		at least two (2) things that will be expectation etations		
4.		n what he/she would do if he/she dec 0=doesn't know, 1=answers but no nber		
5.		n what he/she would do if he/she is e wers but not the most appropriate		- per
6.		n how medications (or treatments) ar wers but not the most appropriate omization procedures		
Ιh	GNATURE: ereby certify that the above swers to items 2,3,4,5 and	ve patient is alert, able to communica 6 above.	5 1	al Score
(E	valuator Signature)	(Date signed)		

Appendix 10 Assessment of Sleep, Mood, Well-being and Cognitive Functioning and Treatment Expectancy

"How did you	sleep last night?"
888	000
Mood & Well-be	eing (treatment period)
"How are you	feeling today?"
888	000
"How is your e	energy level today?"
888	000
Cognitive Functi	ioning (treatment period)
"How is your c	concentration and memory today?"
888	0000
Treatment Exped	ctation (baseline visit only)
"Do you expec	et that the study drug will help you?"
888	000
Treatment Exped	ctation (treatment period)
"Do you think	the drug is helping you?"
888	0000
Treatment Exped	ctation (Day 84 ±2)
"Do you think	you were taking placebo or study drug?"
Placebo	
Study drug	

Sleep (treatment period)

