#### **4.5.4 Other Efficacy Analyses**

##### **4.5.4.1 Sleep, Mood, Well-Being and Cognitive Functioning**

Sleep, mood, cognition and treatment expectation questions will be presented on the AiCure app at selected time points between Day 1 and Day 112 that will appear as random to the participant. Likert scales assessing sleep quality, mood / well-being, and cognitive functioning will be administered via the smartphone (see [Appendix 9](#)). Participant will be instructed to fill in the Likert scales (made of six smiley icons) at defined time points during the trial. In addition, participants will be asked to answer the following question at the end of the study: "Do you think you were taking placebo or drug?".

The Likert scale is a 6-point scale rating values range from 0 to 5. The higher the values, the better is the subjective well-being and cognitive functioning. Hence positive values for change from baseline indicate improvement.

The Likert scale data will be aggregated in 3-weeks intervals, i.e. ≤ Day 1, (Day 1, Day 21], (Day 21, Day 42], (Day 42, Day 63], (Day 63, Day 84], (Day 84, Day 112]. If more than one value is in an interval, the last value in the interval will be used.

The Likert scale scores and change from baseline will be summarized by time interval.

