#### **4.6.3 Clinical Laboratory Tests**

The Investigator will review the laboratory report, document this review, and record any clinically relevant changes occurring during the study in the AE section of the eCRF.

In study **Part A**, hematology, chemistry and lipids are assessed at Week -4, Day 1, Day 14, Day 42, Day 84/EOT, Day 112 (FU). Urinalysis is additionally assessed at Day 28 and Day 56, but not at Day 42. Hematology, chemistry and lipids assessments will be assigned to analysis study days according to the following table:

Assessment Day	Assigned Study Day
>88 or >= 1 day after last study medication	FU, will not be included in statistical analysis
64-88	84
28-63	42
2-28	14
-2-1	1
<-2	-35, will not be included in statistical analysis

Urinalysis assessments will be assigned to analysis study days according to the following table:

Assessment Day	Assigned Study Day
>88 or >= 1 day after last study medication	FU, will not be included in statistical analysis
71-88	84
43-70	56
22-42	28
2-21	14

Clinical laboratory data are stored on the database in the units in which they were reported. For analysis laboratory data will be converted using the International System of Units (SI units; Système International d'Unités). Laboratory data not reported in SI units will be converted to SI units before processing and will be transformed to common reference range using Roche Safety Lab Standardisation.

Summary statistics for converted values and changes from baseline at each assessment time will be presented. Baseline is the patient's last observation prior to initiation of randomized double-blind study treatment.

The number of patients with a laboratory value abnormality in the direction specified (low/high) among patients during randomized double-blind treatment without this abnormality at baseline will be summarized.

Mean (+/- SEM) plots including single values will be presented by scheduled time point and randomized treatment arm.

Safety laboratory test values will be presented by individual listing with flagging of values outside the normal range.

The analysis will be based on the safety analysis population grouped according to the treatment assigned at randomization.

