Abbreviations: BACS = Brief Assessment of Cognition in Schizophrenia, BNSS = Brief Negative Symptom Scale, CGI-I = Clinical Global Impression of Improvement, CGI-S = Clinical Global Impression of Severity, C-SSRS = Columbia-Suicide Severity Rating Scale, DNA = deoxyribonucleic acid, DPAS = Defeatist Performance Attitude Scale, ECB = Effort-choice benefit 18, ECG = Electrocardiogram, EOT = End of treatment, ESRS-A = Extrapyramidal symptom rating scale, abbreviated, FTND = Fagerstrom Test for Nicotine Dependence, IC-PANSS = informant checklist Positive and Negative Syndrome Scale, MINI = Mini International Neuropsychiatric Interview, MTS = most troubling symptom, PANSS = Positive and Negative Syndrome Scale, PK = pharmacokinetic, RBR = Research Biosample Repository, RLWM = Reinforcement learning working memory, SAE = serious adverse event, VRFCAT = Virtual Reality Functional Capacity Assessment Tool, WASI-II = Wechsler Abbreviated Scale of Intelligence – Second Edition, WRAT-4 = Wide Range Achievement Test

RO6889450—F. Hoffmann-La Roche Ltd

48/Technical Document for Statistical Analysis BP40283 PART A

- 1 To decrease patient burden, some assessments may be split within the visit window days. Baseline assessments should be done pre-dose on Day 1 or within 24 hours prior to the first double-blind dose (i.e., on Day -1).
- 2 If treatment is discontinued early, the Week 12 visit assessments as well as the follow-up visit assessments (four weeks after last dose) should be performed.
- 3 Phone calls listed are for scheduled visits. Informal calls by a case manager up to three times per week to follow up with patients, especially during the washout period, are encouraged.
- 4 Eligibility will be confirmed at baseline (see Section [REDACTED]).
- 5 Complete physical exam includes height and weight at screening. Limited physical exams (symptom driven) and weight will be done at subsequent visits including the follow-up visit (see Section [REDACTED]).
- 6 Triplicate ECGs will be performed at screening and a single ECG at subsequent visits ECGs should be performed prior to meals or any scheduled vital sign measurements and blood draws.
- 7 Pregnancy testing will be using a blood sample at screening and urine sample at subsequent visits. If urine test is positive, pregnancy must be confirmed by blood test.
- 8 Washout may start earlier for antipsychotics with long half-life (2 week washout for aripiprazole, olanzapine, see [REDACTED]).

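### SAP 4.4 allows a post-dose Day 1 value as baseline, in conflict with the pre-dose rule in SAP 4.6.3, 4.6.4 and 4.6.9; the app mood, energy and cognition items are the most exposed

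*SAP*

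**What the plan says.** SAP 4.4 gives one baseline definition for all efficacy and safety analyses, the "last non-missing value recorded prior to or on the first day of randomized double-blind study drug administration". It is framed by day and not by time of dose.

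For laboratory tests, SAP 4.6.3 says: "Baseline is the patient's last observation prior to initiation of randomized double-blind study treatment". SAP 4.6.4 (ECG) and SAP 4.6.9 (vital signs, weight) repeat that rule. The sections on BNSS, PANSS, CGI-S and ESRS-A give no baseline rule of their own, so SAP 4.4 is the only one that applies to them.

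For the app items, SAP 4.5.4.1 states that questions are presented "at selected time points between Day 1 and Day 112". Answers are grouped into intervals. The first takes everything up to and including Day 1, and the second starts after Day 1 and ends at Day 21. Within an interval the rule is "If more than one value is in an interval, the last value in the interval will be used". The output is then "The Likert scale scores and change from baseline will be summarized by time interval".

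On conduct, footnote 1 of the schedule in SAP Appendix 2 reads: "Baseline assessments should be done pre-dose on Day 1 or within 24 hours prior to the first double-blind dose". Protocol sections 6 and 8.11.2 likewise place the first dose after the baseline procedures.

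**The concern.** A baseline should be untouched by treatment. If a value recorded after the first dose is used, any acute effect of the drug is built into the reference point. Where the acute and later effects run in the same direction, the drug-placebo difference in change from baseline is then understated.

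There is also a reproducibility problem. A post-dose Day 1 laboratory, ECG or vital-sign value is baseline under SAP 4.4 and on-treatment under the local sections, and the SAP does not say which rule prevails. Two programmers could derive different baselines from the same data.

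The app items matter most because they are not clearly tied to a site visit. They are prompted at times meant to look random to the participant, and all Day 1 answers fall in the baseline interval whatever the hour.

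**Working it through.** The plan states no figure for this point, so the check is mainly a comparison of rules.

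**Step 1. Is a post-dose Day 1 value eligible as baseline?**

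| Measure | Rules that apply | Eligible? | Other protection |
|---|---|---|---|
| Laboratory, ECG, vital signs, weight | SAP 4.4 and the local rule | Yes under 4.4, no under the local rule | Pre-dose conduct instruction |
| BNSS, PANSS, CGI-S, ESRS-A | SAP 4.4 only; their windows assign days -2 to 1 to Day 1 at any hour | Yes | Pre-dose conduct instruction |
| App mood, energy, cognition | SAP 4.4, the interval up to Day 1, and the last-value rule | Yes, and it displaces an earlier answer | None that clearly applies |
| App sleep | Same as above | Yes, but the question is about the previous night | Content is pre-dose |

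**Step 2. Which days are affected?** Day 1 and earlier qualify; Day 2 onward does not. A participant with no answer by Day 1 has no baseline and a missing change score. The problem is therefore confined to the hours of Day 1 after the first dose.

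**Step 3. What happens to the estimate?** Let
- D = drug-placebo difference in mean change with a pre-dose baseline,
- d = acute drug-placebo difference on the item when the Day 1 answer is given,
- p = share of participants whose last Day 1 answer is post-dose, assumed equal in both arms and unrelated to d.

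Under the SAP rule the expected difference is D - p × d. With p between 0 and 1, it lies between D and D - d. The documents give neither p nor d.

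**Step 4. Could there be drug on board?** Protocol section 2.2.2 gives, for healthy volunteers after multiple dosing, a median tmax of 1.07 to 2.50 hours and a terminal half-life of 25.8 to 34.5 hours. If first-dose absorption is similar, an answer later on Day 1 can fall near peak concentration. Assuming one-compartment accumulation, exposure over the first 24 hours as a share of steady state is 1 - 2^(-24/half-life):
- half-life 25.8 h: 1 - 2^(-24/25.8) = 0.475, about 48%
- half-life 34.5 h: 1 - 2^(-24/34.5) = 0.383, about 38%

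Drug exposure on Day 1 is thus real, but it is that of a single dose. It says nothing about whether these items respond within hours.

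**The case against.** The strongest reply is that Day 1 is already controlled. Protocol sections 6 and 8.11.2 and the schedule footnote put baseline procedures before the first dose, and section 8.11.2 puts patient-reported outcomes ahead of other assessments. For scheduled site assessments this stands: no post-dose Day 1 repeat of the BNSS or the other scales is planned. It stands less well for the app items, which are prompted at times that appear random. A conduct instruction also does not decide which recorded value the analysis picks.

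Some stronger inferences are tempting but not supported:

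- *The app baseline must be an on-drug value.* The item labels in Protocol Appendix 10 and SAP Appendix 9 place mood, energy and cognition in the treatment period. But Protocol 8.11.1 starts that period at the IxRS eligibility call, which comes before dosing. The first SAP interval also admits answers before Day 1, and the app-question row in the protocol schedules appears to begin in the placebo compliance period, although the arrow cannot be read with certainty.
- *Safety changes or new abnormalities will be hidden.* Laboratory tests, ECG and vital signs each have the strict local rule. The count of laboratory abnormalities absent at baseline sits in the same section as that rule. Harm would require the general sentence to override the specific ones, which is the less natural reading.
- *The sleep item is affected too.* A Day 1 answer describes the night before the first dose, whatever hour it is entered.
- *Part B is affected.* Part B has its own analysis document, which is not available here.

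**Conclusion.** The point holds as a wording conflict with one practical consequence. SAP 4.4 and SAP 4.6.3, 4.6.4 and 4.6.9 cannot both govern a post-dose Day 1 value. For the app mood, energy and cognition items, the day-based interval and the last-value rule together allow such an answer to replace a pre-dose one. For BNSS, PANSS, CGI-S and ESRS-A the exposure is limited to an unscheduled post-dose Day 1 assessment.

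The bias on an app item is p × d, from none to the full acute effect. It cannot be narrowed, because the documents give neither the share of post-dose answers nor any acute effect on these items. The reading assumes that app prompts are not otherwise held back until dosing order is known.

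Impact is low. Part A stopped with 27 participants randomized, SAP 4 and 4.5 plan no formal hypothesis test, and the app items are listed under other efficacy analyses. No sample-size or power figure depends on this.

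**What to change.** - In SAP 4.4, define baseline as *the latest non-missing value recorded before the first double-blind dose, judged by date and time*. This brings it into line with 4.6.3, 4.6.4 and 4.6.9.
- In SAP 4.5.4.1, apply the same cut to the first interval, and count Day 1 answers given after the dose as on-treatment.
- Where a participant has no pre-dose app answer, show the scores without change from baseline.

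The cost is one changed sentence, one clarification to the app intervals, and a date-time comparison in the programming. The comparison needs times for the app answers and the first dose. If a Day 1 app answer cannot be placed before the dose, it should not be used as baseline. No data collection changes for Part A.
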